1.0 Background & Rationale

Importance of studying added sugars in adolescents. Research that leads to nutritional strategies to prevent T2D in adolescents is an urgent pursuit [1]. One particular contributing factor to the growth of T2D and prediabetes in adolescents is the increased consumption of added sugars. Adolescents in the U.S. have high intakes of added sugars [2-6] which could have poor health implications. Added sugars are found in sugar sweetened beverages and desserts and snacks, top sources of energy for adolescents, and calories from added sugars contribute to 16% of the total energy intake [7, 8]. Levels are well above recommendations from leading scientific organizations, which suggest limiting added sugars to less than 10% of energy [9-12]. However, it is not clear whether sugar reduction to less than 10% of energy is palatable for an adolescent population that prefers sweetened foods and beverages. Moreover, uncertainty about the evidence linking added sugar consumption to risk of disease has made policies that seek to reduce dietary intake of added sugar controversial [13]. The controversy impairs large-scale implementation of recommendations to reduce intake of added sugars by individuals, clinicians, policy makers and industry stakeholders [14].

Evidence linking added sugars and risk of type 2 diabetes and cardiovascular disease lacks information on adolescents. Many epidemiological studies in adults [15-17], but not all [18] show the concept that after controlling for energy intake, high consumption of sugar-sweetened foods is a risk factor for T2D. Epidemiological studies also associate high consumption of added sugars, particularly from sugar sweetened beverages (SSB), with increased adiposity (including central adiposity) and dyslipidemia. These studies formed the basis of recommendations to limit added sugar consumption from the American Heart Organization [9]. The data in youth is limited. Two small randomized studies compared the effects of glucose versus fructose beverages on insulin sensitivity in adolescents and findings were mixed [19, 20]. One longitudinal cohort study showed that higher consumption of added sugars, from SSB, was associated with hyperglycemia and impaired insulin sensitivity in youth aged 8 – 12 years [21]. One study showed that high amounts of added sugars may induce insulin resistance and beta-cell dysfunction and such effects can occur independent of adiposity [22]. ***The literature lacks evidence linking high consumption of added sugars to risk of developing youth-onset T2D.***

Substituting Flavored Sparkling Water for Sugar Sweetened Beverages. Instead of sugar, food manufacturers typically sweeten foods and beverages using low-calorie or artificial sweeteners. “Diet” versions of SSB have been available for several decades and are widely used by adults and children [23]. However the safety of low calorie sweeteners is controversial [24] and many in the scientific and lay communities do not promote their use as a substitute for SSB. We propose that an alternative to SSB may be found in sparkling waters (carbonated water with flavoring, completely unsweetened), which are commercially available in soda-like flavors like cola or [name]™. The rationale for our proposal is the urgent need for an effective strategy to combat adolescent T2D which we will address by demonstrating the benefit of an intervention to reduce added sugars. The objective of the study is to demonstrate whether substituting sparkling water for SSB has benefits for in vivo physiological measures of glycemia while maintaining flavor acceptability to adolescents who are at risk for diabetes.

2.0 Objective(s)

In a prospective, observational 12 week, clinical study in adolescent participants who are high consumers of SSB, we will provide sparkling flavored water to participants and ask them to substitute the drinks for SSB. The objective of the study is to demonstrate whether substituting sparkling water flavored drinks for SSB has glycemic and cardiometabolic benefits while maintaining acceptability to adolescents who are at risk for diabetes.

2.1 Primary Objective

Determine the effect of reducing added sugars intake by substituting carbonated sparkling water on T2D risk in adolescents.

Hypothesis: Adolescents who decrease consumption of SSB by substituting sparkling water will experience decreased blood glucose concentrations and increased insulin sensitivity during an oral glucose tolerance test and decreased glucose excursions during continued glucose monitoring, compared to those who do not decrease consumption of SSB.

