3.0 Outcome Measures/Endpoints

3.1 Primary Outcome Measures

3.1.a Dietary Consumption of SSB and Sparkling Water: We will monitor the adolescents' overall dietary intake using TADA, every two weeks. To assess dietary intake using 4-day food records, we will use the Technology Assisted Dietary Assessment (TADA) system, a mobile app, to acquire food images of eating occasions. TADA was developed at Purdue University and is well suited for the adolescent lifestyle since teens enjoy using mobile technology [25]. We may also assess intake of added sugars by blood biomarkers such as (e.g., $^{13}\text{C}/^{12}\text{C}$ ratio).

3.1.b 2 hour Glucose Concentrations Measured Using 2 hour Oral Glucose Tolerance Testing:

Testing: Oral glucose tolerance testing will be performed at the IU or Purdue Clinical Research Centers, in the morning after participants have undergone an overnight fast for 8 hours. Blood samples will be obtained at -15, 0, 15, 30, 60, 90,120 minutes, relative to ingestion of a glucose drink at a dose of 1.75 g/kg body weight (maximum 75 g glucose). Other primary outcomes will be concentrations of fasting glucose and HbA1c concentrations.

3.1.c. Insulin Sensitivity: For measures of insulin action, which takes into account serum glucose and insulin concentrations, serum fractions from the oral glucose tolerance test will be frozen at -80°C until analysis. Glucose concentrations will be determined using an automated chemistry analyzer (COBAS Integra 800, Roche Diagnostics, Indianapolis, IN); insulin, and c-peptide will be assessed using an Elecsys Systems immunoassay analyzer (Roche Diagnostics). Whole-body insulin sensitivity index (WBISI), the insulinogenic index (IGI), and the oral disposition index (DI) will be calculated as described [26, 27]. The homeostasis model assessment of insulin resistance (HOMA-IR) will be calculated from glucose and insulin concentrations in the fasting state [28]. We will also calculate the HOMA% B and % S values using the HOMA calculator <https://www.dtu.ox.ac.uk/homacalculator/>, which takes into account the variations in hepatic and peripheral glucose.

3.1.d. Glycemic Control Measured Using Continuous Glucose Monitoring: We will collect free-living, glucose measures for 6 consecutive days using the Continuous Glucose Monitoring

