5.0 Study Design

The study design is a prospective observational study in adolescents who are at risk for developing T2D, to evaluate the effectiveness of sparkling water to reduce dietary intake of added sugars and thereby improve glycemia. Study data on consumption and the flavor profile of sparkling water will serve as a measure of acceptability. The study intervention will be to provide carbonated flavored sparkling water for 12 weeks to adolescents who have a usual intake of 2 or more servings of SSB per day and are at a high risk for developing type 2 diabetes. Study measures will be obtained before and after the exposure to carbonated flavored sparkling water and each participant will serve as his/her own control. To encourage the participants to substitute the carbonated flavored sparkling water, study personnel will send them weekly iMessages through the TADA app. In addition, we will monitor the participants' diet, using the TADA app, every two weeks, for 4 days. Study measurements will be obtained at baseline, before the intervention, during and at the end of the 12-week intervention.

Flow diagram for randomized, controlled trial

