Randomization: This is a single arm protocol without randomization of study participants. All participants will be provided the sparkling water. Each participant will serve as his/her own control.

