8.0 Study Calendar

STUDY PROCEDURES	Baseline Study Visit One	Baseline Study Visit Two	Follow-up					Final Study Visit One	Final Study Visit Two
	-2 wk	Day 0	2 wk	4 wk	6 wk	8 wk	10 wk	11 wk	Week 12
Consent/Accent	X								
CGM monitoring	X							X	
TADA Dietary Assessment	X		X	X	X	X	X	X	
Oral Glucose Tolerance Testing		X							X

Cardiometabolic outcomes		X							X
Sensory Testing		X							X

To allow for deviations in terms of timing and scheduling of study visits, we will consider variations of +/- 7 days from the scheduled visit.

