12.0 Statistical Considerations

Power analysis and Estimation of Sample Size: The sample size required for the study is based on the power calculation for the primary outcomes of 2 hour glucose concentrations. Based on preliminary our data from our ongoing DIG IT Study, IU-IRB 1403986016, we show that by reducing added sugars from 9.0% to 6.6% of energy leads to a decrease in 2 hour glycemia of 143.9 ± 9.6 to 123.7 ± 22.6 mg/dL, which is statistically significant and clinically meaningful. Specifically, a sample size of 13 will enable us to detect differences in 2 hr glucose concentrations before and after the intervention, with 80% power and $\alpha = 0.05$. With an expectation of 20% drop out, we will enroll 16 participants.

We will test the data for normalcy and calculate descriptive statistics. Skewed data will be normalized or non-parametric statistics will be used. For Aim 1, changes in glycemia, peak glucose excursions and insulin sensitivity will be assessed using paired T-tests (for normally distributed data). For Aim 2, changes in intensity of sweetness and liking for sparkling water will be assessed using mixed linear models with the participant as a repeated factor. As a secondary analysis we will assess relationship between changes in perceptions of sparkling water, SSB consumption and glycemic measures.

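### The primary hypothesis compares SSB reducers with non-reducers, but the single-arm plan sizes and tests only the pooled before/after change

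*Protocol*

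**What the plan says.** **Hypothesis.** Section 2.1 of the protocol expects lower OGTT glucose, higher insulin sensitivity and smaller CGM excursions in adolescents who replace SSB with sparkling water, "compared to those who do not decrease consumption of SSB". That is a comparison between two kinds of participant.

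**Design.** Section 5.0 says that "each participant will serve as his/her own control". Section 6.0 says "This is a single arm protocol without randomization of study participants", and everyone receives the water.

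**Sizing and test.** Section 12.0 says that "a sample size of 13 will enable us to detect differences in 2 hr glucose concentrations before and after the intervention", with 80% power at alpha 0.05, and enrols 16 to allow for dropout. For Aim 1, "changes in glycemia, peak glucose excursions and insulin sensitivity will be assessed using paired T-tests" when the data are normal; skewed data are transformed or handled non-parametrically.

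**SSB data.** Section 3.1.a lists SSB consumption among the primary outcomes and monitors "overall dietary intake using TADA, every two weeks", by 4-day records. The "TADA Dietary Assessment" row of the Section 8.0 calendar has one baseline entry and six later ones (weeks 2, 4, 6, 8, 10 and 11).

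**Link between SSB and glycemia.** Section 12.0 gives one sentence: "As a secondary analysis we will assess relationship between changes in perceptions of sparkling water, SSB consumption and glycemic measures". The linear modelling in Section 3.3.a concerns other nutrients and physical activity as covariates. The SAP's model has a sensory rating as response and concentration, time and their interaction as terms; it contains neither SSB intake nor glucose.

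**The concern.** The hypothesis and the primary analysis ask different questions. The hypothesis asks whether those who cut SSB improve more than those who do not. The paired test asks whether the average change over everyone is zero. A fall in mean glucose could arise with no difference between reducers and non-reducers, and a difference between them could exist with no change in the overall mean.

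If the plan is followed as written, a significant paired result could be reported as support for a between-person hypothesis, and from there as an effect of reducing SSB. The objective just above the hypothesis in Section 2.1 is worded as an effect, which invites that step. Other explanations for a before/after fall are realistic here: a time trend, or regression to the mean, since Section 4.1 lets participants qualify through raised glucose or HbA1c.

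The one analysis that could speak to the contrast is left open. There are seven diet records per person and several glycemic outcomes. With no stated summary of SSB change and no model, both could be chosen after the data are seen.

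**Working it through.** **1. Texts side by side**

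| Element | Where | Comparison |
|---|---|---|
| Primary hypothesis | Protocol 2.1 | between persons: reducers v. non-reducers |
| Control | Protocol 5.0, 6.0 | within person |
| Sample size | Protocol 12.0 | within person, 2-hour glucose |
| Aim 1 test | Protocol 12.0 | within person, paired |
| SSB change v. glycemia | Protocol 12.0 | between persons; secondary, no model |
| SAP model | SAP, Statistical Model | sensory ratings only |

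The mismatch is complete at this step and needs no arithmetic. What follows shows only what the stated power covers.

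**2. The plan's own figure**

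Inputs from Section 12.0: 143.9 ± 9.6 falling to 123.7 ± 22.6 mg/dL, so a difference of 143.9 − 123.7 = 20.2; n = 13; alpha 0.05. Assumptions: the ± values are SDs (they are not labelled), the test is two-sided, and the before/after correlation r, which is not given, is varied.

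SD of change = √(9.6² + 22.6² − 2r × 9.6 × 22.6) = √(602.92 − 433.92r).

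Paired t-test by noncentral t with 12 df and noncentrality 20.2√13 / SD:

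| r | SD of change | Power, n = 13 |
|---|---|---|
| 0 | 24.55 | 78% |
| 0.078 | 23.86 | 80% |
| 0.5 | 19.65 | 92% |
| 0.75 | 16.66 | 98% |

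The stated 13 is consistent with a before/after test at a small correlation. The match does not identify the formula used: an independent two-sample calculation with pooled SD 17.36 also gives 13, per group. It is the wording of Section 12.0 that ties the 80% to before/after.

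**3. The Section 2.1 contrast at n = 13 (illustration)**

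Further assumptions: 20.2 mg/dL separates the mean changes of the two groups, and reducers to non-reducers split 7/6 or 10/3. None of this is in the documents; the 20.2 is a before/after change in preliminary data.

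Two-sample t on change scores, 11 df, noncentrality 20.2 / (SD_w √(1/n₁ + 1/n₂)). There are two readings of the within-group SD:

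- Reading A: SD_w = SD of change.
- Reading B: the SD of change already includes the gap between groups, so SD_w = √(SD² − p(1 − p) × 20.2²), where p is the fraction of reducers.

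| r | 7/6, A | 7/6, B | 10/3, A | 10/3, B |
|---|---|---|---|---|
| 0 | 27% | 32% | 21% | 23% |
| 0.5 | 39% | 50% | 30% | 35% |
| 0.75 | 51% | 70% | 39% | 50% |

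Worked cell (r = 0, 7/6, A): 20.2 / (24.55 × √(1/7 + 1/6)) = 1.48, giving 27%. Worked cell (r = 0.75, 7/6, B): SD_w = √(16.66² − (7/13)(6/13) × 20.2²) = 13.27, giving 70%.

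The answer moves strongly with the assumed difference. Under reading A, 10.1 mg/dL gives 9% to 17% over the same splits and correlations. At 30.3 mg/dL, a 7/6 split gives 53% to 71% for r from 0 to 0.5.

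**4. Precision if SSB change is kept continuous**

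With 13 people and one covariate, an observed partial correlation of 0.5 has a 95% interval of tanh(0.549 ± 1.96/√9) = −0.10 to 0.83.

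**The case against.** The protocol does not hide its design. Sections 2.0, 5.0 and 6.0 call it observational or single-arm with own controls, and Section 12.0 says that the sized difference is before/after. A careful reader would not take the paired test for a between-person test, and an inability to exclude a time trend belongs to any uncontrolled study; rewording does not cure it. That is fair, and it limits the harm to what is concluded and reported. It does not remove the mismatch, because the hypothesis labelled primary is still the one the primary analysis leaves untested.

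The power figures can also be attacked, and that attack stands. The contrast size, the split and the correlation are all assumed, and the upper end depends on how far the correlation is allowed to go. They illustrate and do not establish the point.

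Three stronger inferences are tempting and are not supported:

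- That the sample size is wrong. The 13 is reproducible for the test it is tied to.
- That SSB intake is not measured. It is a primary outcome with seven scheduled records; only the summary and the model are missing.
- That the remote plan in Section 16 blocks only an SSB-change analysis. Its sessions describe no OGTT, so remote-only participants drop out of every OGTT-based analysis, the paired test included.

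**Conclusion.** The concern holds as an inconsistency between the stated primary hypothesis and the analysis meant to answer it. The paired test does not address reducers versus non-reducers and cannot credit a change to SSB reduction. The secondary sentence in Section 12.0, the covariate modelling in Section 3.3.a and the SAP do not fill the gap. This rests on the text alone.

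Its size in power terms is indicative only: about 21% to 70% for the contrast under the assumptions in the working, against a stated 80% that applies to the before/after test. The change should be made because it alters what the trial may conclude. The before/after analysis itself is coherent and can stand.

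**What to change.** Issue a dated amendment that states which data had already been analysed, and choose one route.

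**(a)** Restate the Section 2.1 hypothesis as a within-person change from week 0 to week 12, and limit the conclusion to that change, not to an effect of reducing SSB.

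**(b)** Keep the between-person hypothesis, state that the paired test does not test it, and base any conclusion about it on the secondary analysis already planned. Specify that analysis in the SAP for each outcome in Section 2.1: OGTT glucose, insulin sensitivity and CGM excursions. One workable form is a regression of the change in the outcome on the change in SSB intake from the TADA records, adjusted for the baseline outcome. Define the SSB summary in advance; more than one choice is defensible. State that a slope is a different estimand from a reducer/non-reducer contrast, and report it with a 95% interval as observational and imprecise.

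Under either route, keep the paired test as the sized analysis and say that the 80% power applies only to it.

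**Cost.** No new visits or measurements are needed, since the TADA records, OGTT and CGM are already scheduled. The amendment would be late: the SAP is in the past tense, so the sensory data appear to have been analysed, and the documents do not show whether the glycemic data have been. Route (a) narrows the conclusion and route (b) yields a wide interval. Participants seen only in the Section 16 remote sessions contribute no OGTT endpoint to (a), (b) or the paired test.

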2.2 Secondary Objective

Determine the acceptability of sparkling water with no added sugars in adolescents.

Hypothesis: After consuming sparkling water flavored drinks for 12 weeks, adolescents' acceptance of the flavor profile of the drinks will improve.

2.3 Description of the Intervention to Reduce Intake of SSB by substituting carbonated flavored seltzer water:

To encourage participants to substitute sparkling water flavored water for SSB intake, we will provide enough supplies of the drinks to adolescents (and their families) each month. We will also provide iPhones with the TADA app to the adolescent participants. Study staff will remind participants to consume the sparkling water through iMessages sent through the TADA app.

3.0 Outcome Measures/Endpoints

3.1 Primary Outcome Measures

3.1.a Dietary Consumption of SSB and Sparkling Water: We will monitor the adolescents' overall dietary intake using TADA, every two weeks. To assess dietary intake using 4-day food records, we will use the Technology Assisted Dietary Assessment (TADA) system, a mobile app, to acquire food images of eating occasions. TADA was developed at Purdue University and is well suited for the adolescent lifestyle since teens enjoy using mobile technology [25]. We may also assess intake of added sugars by blood biomarkers such as (e.g., $^{13}\text{C}/^{12}\text{C}$ ratio).

3.1.b 2 hour Glucose Concentrations Measured Using 2 hour Oral Glucose Tolerance Testing:

Testing: Oral glucose tolerance testing will be performed at the IU or Purdue Clinical Research Centers, in the morning after participants have undergone an overnight fast for 8 hours. Blood samples will be obtained at -15, 0, 15, 30, 60, 90,120 minutes, relative to ingestion of a glucose drink at a dose of 1.75 g/kg body weight (maximum 75 g glucose). Other primary outcomes will be concentrations of fasting glucose and HbA1c concentrations.

3.1.c. Insulin Sensitivity: For measures of insulin action, which takes into account serum glucose and insulin concentrations, serum fractions from the oral glucose tolerance test will be frozen at -80°C until analysis. Glucose concentrations will be determined using an automated chemistry analyzer (COBAS Integra 800, Roche Diagnostics, Indianapolis, IN); insulin, and c-peptide will be assessed using an Elecsys Systems immunoassay analyzer (Roche Diagnostics). Whole-body insulin sensitivity index (WBISI), the insulinogenic index (IGI), and the oral disposition index (DI) will be calculated as described [26, 27]. The homeostasis model assessment of insulin resistance (HOMA-IR) will be calculated from glucose and insulin concentrations in the fasting state [28]. We will also calculate the HOMA% B and % S values using the HOMA calculator <https://www.dtu.ox.ac.uk/homacalculator/>, which takes into account the variations in hepatic and peripheral glucose.

3.1.d. Glycemic Control Measured Using Continuous Glucose Monitoring: We will collect free-living, glucose measures for 6 consecutive days using the Continuous Glucose Monitoring

(CGM; FreeStyle Libre Pro System; Abbott; Abbott Park, IL[29]. The CGM will be administered to participants 6 days before the start of Week 0 and Week 12, and the monitor will be removed at the clinic visit. For the placement of the CGM, the back of the participant's upper arm will be cleaned with an alcohol wipe and dried. The sensor will be firmly adhered to the arm with the needle application inserted. The FreeStyle sensor measures glucose every 15 sec and records an average glucose value every 15 min for up to 14 days.

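### At least twelve measures are labelled primary, only 2-hour glucose is powered, and neither document states a deciding outcome or a multiplicity rule

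*Protocol*

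**What the plan says.** Protocol Section 3.1 lists the following under its primary heading:

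- **3.1.a, two measures:** intake of sugar-sweetened beverages (SSB) and of sparkling water ("3.1.a Dietary Consumption of SSB and Sparkling Water"). A blood biomarker of added sugar is optional and is not counted here.
- **3.1.b, three measures:** 2-hour glucose ("3.1.b 2 hour Glucose Concentrations Measured Using 2 hour Oral Glucose Tolerance Testing"), then fasting glucose and HbA1c ("Other primary outcomes will be concentrations of fasting glucose and HbA1c concentrations").
- **3.1.c, six measures:** "Whole-body insulin sensitivity index (WBISI), the insulinogenic index (IGI), and the oral disposition index (DI) will be calculated"; "The homeostasis model assessment of insulin resistance (HOMA-IR) will be calculated"; and "We will also calculate the HOMA% B and % S values using the HOMA calculator".
- **3.1.d, at least one measure:** "3.1.d. Glycemic Control Measured Using Continuous Glucose Monitoring", with no summary measure defined.

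Section 12.0 powers one of these: "The sample size required for the study is based on the power calculation for the primary outcomes of 2 hour glucose concentrations". Even that sentence speaks of primary outcomes in the plural. For Aim 1, Section 12.0 plans paired t-tests on three groups of measures: glycemia, peak glucose excursions and insulin sensitivity. An alpha of 0.05 appears only in the sample-size statement. The section gives no hierarchy, deciding outcome or multiplicity rule.

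The hypothesis in Section 2.1 joins lower OGTT glucose, higher insulin sensitivity and smaller glucose excursions on continuous monitoring with the word 'and'.

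The SAP models sweetness and liking ratings, which belong to the secondary outcomes. It contains no analysis of any primary outcome.

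**The concern.** When many outcomes share the primary label and no rule ranks or combines them, the result that answers the primary objective can be chosen after the data are seen. Nothing in either document stops a report from leading with whichever glycemic or insulin index moved and calling it primary. The plan also does not say what conclusion follows if 2-hour glucose shows no change but, say, HOMA-IR does.

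This matters because the protocol does not present itself as purely exploratory. Section 2.0 sets out to demonstrate glycemic benefit, and Section 12.0 claims 80% power. A reader will attach that power to anything called primary, but it was calculated for 2-hour glucose only.

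**Working it through.** **1. Count.** 3.1.a gives 2, 3.1.b gives 3, 3.1.c gives 6 and 3.1.d gives at least 1, so 2 + 3 + 6 + 1 = 12. Without the two intake measures, which have no stated test of change, 12 − 2 = 10 glycemic or insulin measures remain. Because continuous monitoring has no defined summary measure, 10 is a minimum.

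**2. The plan's own figure.** Inputs from Section 12.0: 2-hour glucose falls from 143.9 ± 9.6 to 123.7 ± 22.6 mg/dL, with power 80% and alpha 0.05.

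- Assumptions: the ± values are SDs, the test is two-sided, and the within-person correlation r, which is not given, is varied.
- Change: 143.9 − 123.7 = 20.2 mg/dL.
- SD of change = √(9.6² + 22.6² − 2·r·9.6·22.6). At r = 0 this is 24.55; at r = 0.1 it is 23.65.
- Paired t-test by the noncentral t distribution: n = 14 at r = 0, 13 at r = 0.1, and 12 at r = 0.2.

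The stated 13 is reproduced for one outcome tested at 0.05. Sixteen enrolled with 20% dropout leaves 16 × 0.8 = 12.8, about 13.

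**3. False positives if the ten measures were each tested at two-sided 0.05 and any one counted.** Under independence:

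- any direction: 1 − 0.95¹⁰ = 0.401
- favourable direction only: 1 − 0.975¹⁰ = 0.224

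For correlated outcomes, equicorrelated normal test statistics were simulated with no true effect and a cut-off of 1.96:

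| Assumed correlation | Any direction | Favourable only |
|---|---|---|
| 0 | 40% | 22% |
| 0.5 | 29% | 14% |
| 0.8 | 17% | 9% |

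The nominal rates are 5% and 2.5%. Even at 0.8 the rate is more than three times nominal (17/5 = 3.4; 9/2.5 = 3.6). Simulated paired t-tests at n = 13 give 30% in place of 29% at correlation 0.5, so the normal approximation is adequate.

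**4. Sensitivity to the reading.** Taking Section 12.0's three groups as three tests, with any one sufficient, gives 1 − 0.95³ = 14% if independent. If all three had to succeed, the error with no true effect anywhere would be below 1% at correlations up to 0.8. The documents choose none of these rules.

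**5. Cost of the alternatives.** With 2-hour glucose as the sole primary outcome, alpha stays 0.05 and n stays 13. With all twelve kept primary under Bonferroni, alpha is 0.05/12 = 0.0042. At r = 0.1, 2-hour glucose would then need 23 evaluable participants, and power at n = 13 would be about 38%.

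**The case against.** A reader might infer that each primary measure is tested at 0.05, that success on any one meets the primary objective, and that a chance success is therefore likely. The documents do not support that reading.

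- Alpha is stated once, for sizing 2-hour glucose. The intake measures have no stated test of change.
- No any-one rule is written. The Section 2.1 hypothesis is conjunctive, and an all-must-succeed reading would make the error very small.
- Every figure in the table is below one half. Independence is implausible, because the HOMA indices share fasting samples and the other indices come from the same OGTT.

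It can also be said that Section 3.1.c only lists indices to be calculated under one heading, and that 2-hour glucose is implicitly primary because it has its own heading and sets the sample size.

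These points limit the claim but do not remove it. Section 3.1.b expressly names further primary outcomes, so 2-hour glucose is not the only one as written. The conjunctive hypothesis is not turned into a decision rule anywhere. Correlation lowers the error but leaves it above nominal throughout the range examined.

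Two further objections stand in full. The single-arm pre-post design exposes every one of these tests to regression to the mean and time trends. In addition, one route into the study is a 2-hour glucose of 140–199 mg/dL (Section 4.1), so some participants may be selected on the very outcome proposed as sole primary. Multiplicity therefore cannot be called the main source of a false claim here, and relabelling does not address that bias.

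**Conclusion.** The point holds as a gap in the decision rule: at least twelve primary measures, one powered, none named as deciding, no multiplicity rule, and an SAP that does not cover them. If the ten glycemic and insulin measures were each tested at two-sided 0.05 and any one were taken as success, the false-positive rate would be about 17% to 40%, or 9% to 22% in the favourable direction. Those ranges rest on both conditions, which the documents do not state, and on assumed equal correlations of 0 to 0.8, since the documents give none. The plan should be changed, but the documents do not show that a false primary success is the probable result.

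**What to change.** In Protocol Sections 3.1 and 12.0, name change in 2-hour OGTT glucose (Week 12 minus Day 0) as the single primary outcome, tested at two-sided 0.05. Move fasting glucose, HbA1c, the insulin indices and continuous glucose monitoring to secondary. Report these with estimates and 95% confidence intervals, and state that none of them alone supports a claim of success on the primary objective. Keep SSB and sparkling-water intake as adherence measures. Add the matching glycemic analysis to the SAP, which has none now.

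The sample-size basis is unchanged and no alpha correction is needed. The costs are:

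- Insulin sensitivity and glucose excursions, which are part of the Section 2.1 hypothesis, become supportive.
- Participants followed only under the Section 16.0 remote plan, which describes no OGTT, would not contribute to the primary analysis. Their number should be reported.
- The SAP is written in the past tense. If the glycemic data have already been analysed, the choice must be reported as made after the fact, with the Section 12.0 sample-size statement as its justification.
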